STATISTICAL ANALYSES

Data Analysis Plan: The distributions of all continuous variables will be checked for normality, and transformations will be employed (if necessary) before applying specific parametric techniques. Before performing specific analyses, we will examine all outcomes for outliers. All statistical comparisons will be two-sided and the critical level for rejection of the null hypothesis will be considered to be a p-value of < 0.05 . Where needed, False Discovery Rate Analysis will be used to adjust critical p values to control for multiple comparisons. Any comparison where homogeneity is violated will not be considered significant. Means, standard deviations, proportions, and 95% confidence intervals will be used to describe all continuous variables.

Dropouts and Missing Data: As this is an inpatient laboratory study within a controlled setting, we expect only minimal intermittent missing data, though we do expect to have some subjects drop out without completing all of the experimental conditions. We will use all available data from subjects prior to drop-out. We will account for missing data directly using mixed-effects models (MEM) (Diggle et al. 2002). MEMs do not require complete measurements to estimate effects and inferences are valid provided that data are “missing at random” (Little & Rubin, 2002). ‘Missing at random’ (i.e. the missing mechanism does not depend on the value of the unobserved outcome) is un-testable in most medical research and in our study as well. One can assume either parametric or semi-parametric models for the missingness that does depend on the unobserved outcome value and do the analysis (Diggle and Kenward 1994, Kenward 1998). Comparison of the inferences from assuming various models for the missingness provides a measure of the validity of the efficacy estimate from the model that assumes missing ‘at random’. One can also compute a local sensitivity index which measures the change in the estimated treatment effect in a neighborhood of the ‘missing at random’ model for missingness (Rotnitzky et al. 1998). We will perform sensitivity analyses based on these two approaches to assess the effect of the assumption of missing ‘at random’ on the inference.

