To approximate a suitable number of subjects for a traditional hypothesis-testing approach, a power analysis was conducted using G* Power 3.1.7. Estimates of the magnitude of the medication effect on withdrawal were estimated using a previous study that assessed naloxone-precipitated withdrawal (Jones et al., 2016). Based on these data we calculated a Cohen's D effect size of .75, which constituted a 15-point difference (mean SD of 20) in total withdrawal score (0-125) between any two dose conditions. Applying this to the current proposal, a total sample size of 16 completers should provide 90% power to detect this difference at a p of < 0.05 . Sixteen completers will provide 88% power to detect a 10-mm difference in positive subjective effects, e.g. "Liking" on a 100-mm VAS scale (alpha of 0.05). This analysis assumes a SD of 12 mm and a Cohen's D effect size of 0.84 based on previous visual analog scale assessments of abuse liability of opioids and cannabinoids (Cooper et al., 2018, Jones et al., 2017).

Due to the exploratory nature of this study, effect size estimates will be the main research outcome for the secondary aims, along with the interpretation of confidence interval lengths and degree of overlap to indicate precision and degree of difference (i.e., threshold of clinical importance) between dose conditions (respectively). A sample size of 16 completers was determined to be sufficient to obtain precise 95% confidence intervals with a margin of error of at most 25%. Thus, with regard to the detection of differences in all the study aims, these calculations suggest that this study is suitably powered.

Sex as a Biological Variable

Sex-specific comparisons will be performed to provide an indicator of a Sex x Treatment interaction. The within-subject nature of the study's design should control for potential sex differences. Though not powered to specifically detect sex differences, we are still in compliance with NIH policies to enroll males and females. Furthermore, sex as a biological variable will be examined and reported in accordance with NIH policy (https://orwh.od.nih.gov/sites/orwh/files/docs/NOT-OD-15-102_Guidance.pdf).

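### Secondary aims: degree of difference between dose conditions is gauged by overlap of confidence intervals, which, read as one interval per condition, ignores the within-participant pairing

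*SAP*

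**What the plan says.** In the SAP's Power section, the paragraph on the exploratory aims states that "effect size estimates will be the main research outcome for the secondary aims". These come with "interpretation of confidence interval lengths and degree of overlap to indicate precision and degree of difference" between dose conditions. Length is paired with precision and overlap with degree of difference, which the SAP glosses as a threshold of clinical importance. The paragraph puts the margin of error at no more than 25%: "A sample size of 16 completers was determined to be sufficient to obtain precise 95% confidence intervals with a margin of error of at most" that figure. It closes by claiming adequate power to detect differences in all the study aims.

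The design is a crossover. The protocol (Study Procedures, Laboratory Testing) gives each participant all six combinations, and the SAP (Sex as a Biological Variable) says: "The within-subject nature of the study's design should control for potential sex differences".

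No interval for a within-participant difference is specified. The Data Analysis Plan uses intervals descriptively: "Means, standard deviations, proportions, and 95% confidence intervals will be used to describe all continuous variables".

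Under Aims, Outcome Measures, and Hypotheses, the methods named for the secondary aims are:

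- Adverse events (number and severity): generalized mixed model with participant as a random effect.
- Pupil diameter: repeated-measures ANOVA.
- Physiological parameters (same aim as adverse events): none.
- Liking and Good Effect: none.

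**The concern.** In a crossover the uncertainty that matters is that of each participant's difference between two conditions. An interval around a single condition's mean reflects the spread between participants, much of which cancels in the difference. Laying two such intervals side by side therefore overstates the uncertainty of the comparison. Even without correlation it is too strict, because it adds the two standard errors instead of combining them in quadrature.

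The risk is that a real difference is described as small or absent because the intervals overlap. That matters most for Liking and pupil diameter, where the SAP hypothesises no significant difference, so overlap could be misread as support. For Liking, the result at stake is an abuse-potential signal of the size the SAP planned to detect.

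**Working it through.** **Inputs from the SAP.** Power section: "Sixteen completers will provide 88% power to detect a 10-mm difference in positive subjective effects" and "This analysis assumes a SD of 12 mm and a Cohen's D effect size of 0.84", alpha 0.05. Data Analysis Plan, with 0.05 as the level: "All statistical comparisons will be two-sided and the critical level for rejection of the null hypothesis will be considered to be a p-value of <" that level. **Assumption:** the correlation r between a participant's values under two conditions is not in the documents, so it is varied from 0 to 0.7.

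**Step 1: reproduce the 88%.** Two-sided paired t-test, n = 16, df = 15, noncentrality 0.84 × √16 = 3.36, critical t = 2.131: power 88.1%. With d = 10/12 = 0.833 it is 87.6%. Alternatives do not fit: one-sided paired t 94%; normal approximation 92%; two independent groups of 16, Φ(0.84 × √8 − 1.96) = Φ(0.416) = 66%. The SAP's figure is a paired calculation.

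**Step 2: which intervals are meant.** Overlap between dose conditions needs an interval for each condition. The 25% margin fits this reading: 1.96 × √(0.25/16) = 0.245, the half-width for a proportion in one condition. This is an inference, not a statement in the SAP.

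**Step 3: observed difference needed, SD 12 per condition.**

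- Each condition's half-width: 2.131 × 12/√16 = 6.39 mm. Non-overlap needs about 2 × 6.39 = 12.8 mm, more than the 10 mm planned for.
- Paired interval excludes zero at 2.131 × 12 × √(2(1 − r))/4: 9.0 mm (r = 0), 7.6 (0.3), 6.4 (0.5), 5.0 (0.7).

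**Step 4: the other reading of SD 12.** If it is the SD of differences, as the 88% calculation uses it, the per-condition SD is 12/√(2(1 − r)) = 8.5, 10.1, 12.0, 15.5 mm. Non-overlap then needs about 9.0, 10.8, 12.8, 16.5 mm, against 6.4 mm for the paired interval.

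**Step 5: simulated detection of a true 10 mm difference.** 1,000,000 bivariate-normal trials per cell, n = 16. Hidden is the share of trials with a paired interval excluding zero in which the per-condition intervals still overlap.

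| r | SD 12 per condition: non-overlap | paired | hidden | SD 12 of differences: non-overlap | paired | hidden |
|---|---|---|---|---|---|---|
| 0 | 28.6% | 59.7% | 52% | 63.6% | 87.6% | 27% |
| 0.3 | 25.7% | 75.0% | 66% | 42.6% | 87.6% | 51% |
| 0.5 | 23.2% | 87.6% | 74% | 23.2% | 87.5% | 73% |
| 0.7 | 20.1% | 98.0% | 79% | 5.5% | 87.6% | 94% |

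With no true difference, strict non-overlap occurs in 0.5% of trials at r = 0 and 0.03% at r = 0.5, against the nominal 5%.

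**Step 6: larger effects.** At r = 0.5, non-overlap detects 44% at 1.0 SD, 75% at 1.25 SD and 94% at 1.5 SD (per-condition SD).

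**The case against.** **Overlap is not the only method.** A reader might infer that it decides all secondary aims. It does not: adverse-event number and severity and pupil diameter have within-participant models, the 0.05 level applies to all comparisons, and the pupil and Liking hypotheses are worded in terms of significance. The missing-data paragraph also promises mixed-effects models in general. This stands. What remains is that overlap sits beside those models with no rule for which prevails, and that no model is tied to Liking/Good Effect or the physiological parameters.

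**The SAP sets no yes/no rule.** It speaks of degree of overlap in an exploratory study, so the detection rates above test a stricter criterion than the one written. This also stands. But a graded reading uses the same unpaired intervals and has no cut-off, and the same paragraph claims power to detect differences.

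**A reader might infer that most real differences would be hidden.** The documents do not support that in general. It depends on r, on which SD the 12 mm is, and on effects near the planned size. The hidden share is 27% in the mildest case, and differences of about 1.5 SD are mostly seen. Pupil and Liking are change scores, so r may be lower than for raw values. The normal model does not describe adverse-event counts.

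**A reader might infer that the method favours the study's hypotheses.** It does so only for the two no-difference hypotheses. Insensitivity works against the adverse-event hypothesis, which expects differences. Treating non-significance as equivalence is a separate problem that paired tests would not cure.

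**Conclusion.** The concern holds in limited form. On its natural reading, the overlap criterion ignores the pairing and is inconsistent with the paired test that yields the SAP's 88%. The gap is full for Liking/Good Effect and the physiological parameters. For adverse events and pupil diameter it is a competing, weaker yardstick. Under a strict reading on the Liking inputs, non-overlap is less sensitive than the paired interval in every case examined. The loss runs from 24 percentage points (63.6% against 87.6%) to 82 points (5.5% against 87.6%). These sizes rest on the per-condition reading of the intervals, an assumed r of 0 to 0.7 and normal data. They are upper illustrations for a graded use of overlap. The aims are secondary and exploratory, so the matter should be corrected but does not touch the primary analysis.

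**What to change.** In the SAP's Power section, replace overlap with the estimated within-participant difference and its 95% confidence interval for each contrast the hypotheses need:

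- each active V-MJ dose versus 0 mg within each naloxone level;
- for adverse events, also each combination versus double placebo.

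Take these from the models already named, on the model's own scale for adverse-event counts (a rate ratio, for example). For Liking/Good Effect and the physiological parameters, name a linear mixed model with participant as a random effect. State that neither overlapping intervals nor an interval that includes zero is evidence of no difference. The SAP gives no margin for judging equivalence, so a no-difference claim would need one set in advance.

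The contrasts are written for the protocol's conditions. The SAP still names dronabinol and other dose levels, and the two documents must be reconciled before the contrasts are listed.

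The cost is a few sentences and slightly more analysis work, with no added participants, sessions or data.

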#### Gender, Racial and Ethnic Breakdown

All efforts will be made to ensure that the representation of women and of ethnic minorities are in proportion to the individuals with Opioid Use Disorder (OUD) in New York City. It is estimated that the sample will be 70% male, 50-40% Caucasian, 45%-40% Black or African American, 0-5% Asian, Pacific Islander and Native American, and 15% will self-identify as multi-racial. We anticipate that  $\approx$  30% of our sample will be of Latino/Hispanic ethnicity. These estimates are based upon data from non-crisis heroin treatment admissions, reported by the New York City Department of Health and Mental Hygiene. <https://ndews.umd.edu/sites/ndews.umd.edu/files/SCS-Report-2018-New-York-City-FINAL.pdf>.

Description of subject population

Healthy participants meeting DSM-5 OUD criteria and physical dependence on opioids will be enrolled.

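### Separate comparisons within each sex are to stand in for a sex-by-treatment interaction, and nothing in the SAP estimates the difference in treatment effect between the sexes

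*SAP*

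**What the plan says.** The SAP section Sex as a Biological Variable gives the whole sex analysis in a few sentences. The method is: "Sex-specific comparisons will be performed to provide an indicator of a Sex x Treatment interaction". It continues: "The within-subject nature of the study's design should control for potential sex differences". It then concedes the limit on power ("Though not powered to specifically detect sex differences") and commits to examining and reporting sex under NIH policy. It names no interaction term, contrast or model, and it does not say what pattern in the separate results would count as an interaction.

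Elsewhere in the SAP, the primary aim is analysed by repeated-measures ANOVA across dose conditions, with no sex factor. The Data Analysis Plan sets the general rule: "All statistical comparisons will be two-sided and the critical level for rejection of the null hypothesis will be considered to be a p-value of" less than 0.05. False discovery rate adjustment is to be used where needed, but is not tied to the sex comparisons.

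The protocol, under Gender, Racial and Ethnic Breakdown, gives the expected mix: "It is estimated that the sample will be 70% male".

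**The concern.** An interaction is a difference between two treatment effects. To see it, one needs an estimate of that difference and its standard error. Analysing men and women separately gives neither. If the separate results are read by their p-values, the same true effect can easily be significant in one sex and not in the other, because each subgroup is small. The report could then say that men respond and women do not when nothing of the kind is true.

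The sentence that the within-subject design deals with sex differences adds to the problem. Using each person as their own control removes the main effect of sex, meaning a constant difference in level between men and women. It does not remove a sex difference in response to treatment, which is the interaction named one sentence before.

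**Working it through.** **Inputs**
- Planning effect, primary outcome (SAP, Power): "we calculated a Cohen's D effect size of .75, which constituted a 15-point difference (mean SD of 20) in total withdrawal score (0-125").
- Sample size and power: "a total sample size of 16 completers should provide 90% power to detect this difference".
- Second planning effect: "Sixteen completers will provide 88% power to detect a 10-mm difference in positive subjective effects", with d = 0.84.
- Level: two-sided 0.05 (SAP, Data Analysis Plan).
- Sex split: 0.70 × 16 = 11.2, taken as 11 men and 5 women. This is an assumption, because the protocol's 70% is an estimate for the sample and not a figure for completers.

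**The SAP's own figures first.** Power is from the paired t-test (noncentral t, n − 1 df), with d as the effect size of the within-person difference. For n = 16 and d = 0.75 it is 80.1% two-sided and 88.8% one-sided, so the stated 90% is approached only one-sided on this reading. For d = 0.84 it is 88.1% two-sided, which matches the stated 88%. If SD 20 is instead a per-condition SD, the effect size becomes 0.75/√(2(1 − ρ)), where ρ is the within-person correlation. Two-sided power is then 88.0% at ρ = 0.6 and 95.1% at ρ = 0.7, so 90% would need a ρ between these. The SAP states no ρ.

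**How often exactly one sex is significant.** Take the same true effect in both sexes, one contrast, d = 0.75 and two-sided 0.05. Power is 0.612 in 11 men and 0.254 in 5 women. Then

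P(exactly one significant) = 0.612 × (1 − 0.254) + 0.254 × (1 − 0.612) = 0.4566 + 0.0986 = 0.555.

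A simulation of 200,000 trials gave 0.556. At d = 0.84 the figure is 58.2%.

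**Dependence on the true common effect** (11/5, two-sided)

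| d | 0 | 0.3 | 0.5 | 0.75 | 1.0 | 1.25 | 1.5 |
|---|---|---|---|---|---|---|---|
| exactly one sex significant | 9.5% | 20.5% | 37.3% | 55.5% | 56.9% | 44.3% | 29.2% |

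The rate exceeds 50% only for d of about 0.66 to 1.15. Its maximum is 58.6%, near d = 0.89.

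**Dependence on ρ, if SD 20 is per condition** (11/5, two-sided, 15-point effect)

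| ρ | 0 | 0.3 | 0.5 | 0.6 | 0.7 | 0.8 |
|---|---|---|---|---|---|---|
| effect size of the difference | 0.53 | 0.63 | 0.75 | 0.84 | 0.97 | 1.19 |
| exactly one sex significant | 40.0% | 48.5% | 55.5% | 58.2% | 57.7% | 48.1% |

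**Dependence on the split** (d = 0.75): 8/8 gives 49.5%, 10/6 gives 52.2%, 11/5 gives 55.5% and 12/4 gives 59.9%. Drawing the number of men as Binomial(16, 0.7) gives 57.9%. Going from 8/8 to 11/5 adds 55.5 − 49.5 = 6.0 points.

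**The direct comparison.** This is a two-sample t-test of the within-person differences, men against women, with 14 df. Its simulated false-positive rate is 5.0%. The 95% half-width is 2.145 × √(1/11 + 1/5) = 2.145 × 0.539 = 1.16 SD of the within-person difference. That is about 23 points if this SD is 20, which is more than the 15-point planning effect. Power is 25% for a between-sex difference of 0.75 SD, and reaches 81% only at 1.65 SD.

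**The case against.** The strongest reply is that the SAP never says an interaction will be inferred when one sex is significant and the other is not. It speaks only of an indicator. Its Power section calls the study exploratory and, for the secondary aims, puts effect sizes, interval lengths and overlap first. The sex results might be read the same way. This stands: the 56% belongs to an assumed reading, although the two-sided 0.05 rule for all comparisons makes that reading a natural one. It does not clear the plan, because on the estimate-based reading there is still no interval for the difference between the sexes.

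A reader might infer that the method would suggest a false interaction in more than half of trials whatever the truth. The documents do not support that. The figure needs the significance reading, a single contrast, and a common effect of about 0.66 to 1.15 SD; on the per-condition reading of SD 20 it also needs a favourable correlation. A reader might also blame the unequal numbers of men and women. An 8/8 split still gives 49.5%, so low power within each sex is the main cause.

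The SAP's admission that it is not powered for sex differences is fair, but it addresses real differences being missed. It does not address differences that appear by chance. Finally, sex is in no aim, hypothesis or sample-size target, so no primary or secondary conclusion depends on it. That limits the weight of the point.

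**Conclusion.** The concern holds in a conditional form. The SAP offers separate comparisons as its indicator of an interaction and nowhere estimates the difference in treatment effect between the sexes. Read by significance, at the SAP's planning effect of d = 0.75 (as a within-person effect size, equal in both sexes, one contrast, 11 men and 5 women), exactly one sex would be significant in about 56% of trials with no interaction, against 5% for a direct test. The 56% should not be quoted without those conditions. For the 11/5 split, two-sided, and common effects from 0 to 1.5 SD, the lowest rate found is 9.5%, at d = 0. The number of contrasts to be examined by sex is not stated, so a rate over the whole sex analysis cannot be given.

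The sentence on the within-subject design is right for the main effect of sex and wrong if taken to cover treatment response. This is a worthwhile correction to an exploratory analysis and does not threaten the primary aim.

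**What to change.** 1. Add sex and sex by dose condition to the model for the primary outcome. The SAP names repeated-measures ANOVA under the primary aim and mixed-effects models under Dropouts and Missing Data. Sex can enter the first as a between-subject factor and the second as a fixed effect, but the SAP should say which model is used.
2. Name one contrast for the sex analysis. With the protocol's six conditions, the sex-by-condition term has (2 − 1) × (6 − 1) = 5 df and gives no single estimate. An example in the protocol's terms is naloxone 4 mg + V-MJ 25 mg against naloxone 4 mg + V-MJ 0 mg. The SAP's Randomization paragraph lists a different product and different doses, so the two documents must be reconciled before the contrast is fixed.
3. Report the between-sex difference in that contrast with its 95% CI and label it exploratory. Show sex-specific estimates descriptively only, and base no claim on subgroup p-values.
4. Reword the within-subject sentence to say that the design removes the main effect of sex but not a sex difference in treatment response.

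The cost is a model term and a few SAP sentences, with no new data or participants. The downside is that the interval will be wide (half-width about 1.16 SD) and power low (about 25% for a 0.75 SD difference between the sexes). That is an honest account of what 16 completers can show.
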